Effect of Medical Marijuana on Neurocognition and Escalation of Use

NCT03224468

Date: 1/28/2022

PARTNERS HUMAN RESEARCH COMMITTEE

DETAILED PROTOCOL: Effect of Medical Marijuana on Neurocognition and Escalation of Use

Protocol #: 2015P001600

Principal Investigator: [name].

Co-Investigator: A. [name]

Summary of Changes Made and Rationale

The IRB protocol, attached, was written for a pilot phase of the trial, and was updated when we received the R01. All measures, outcome definitions, and sample size calculations were up to date in clinicaltrials.gov (NCT03224468). The statistical analysis section was amended before any data were analyzed except for the propensity score analysis for missing data, explained below. No changes were made after looking at the data, except for the propensity score analysis.

Method of randomization:

In Year 1 of the study, we realized that many participants, who were interested in obtaining an MMC never obtained one because of barriers such as expense or needing to go outside the usual healthcare system. We therefore changed our randomization from 1:1 to 2:1 MMC:WLC early in the trial in order to have enough participants in the MMC arm.

Outcomes and outcome definitions:

Outcome measures and definitions were updated on 07/19/2017 in clinicaltrials.gov (NCT03224468), but were not explicitly stated in the IRB protocol.

Primary Outcome Measures:

- Cannabis Use Disorder Symptoms (*Time Frame: Baseline to 12 Weeks*)
 - o The DSM-5 Cannabis Use Disorder Checklist will evaluate symptoms of CUD (number of symptoms).
- Changes in Symptoms of Depression and Anxiety (*Time Frame: Baseline to 12 Weeks*)
 - o For those with depression and anxiety symptoms, the Hospital Anxiety and Depression Scale will be used to assess symptoms.
- Changes in Pain (*Time Frame: Baseline to 12 Weeks*)
 - o For those with pain, the Brief Pain Inventory Severity Scale (BPI-S) will be used to assess levels of pain.
- Changes in Sleep (*Time Frame: Baseline to 12 Weeks*)
 - o For those with insomnia, the Athens Insomnia Scale will be used to assess symptoms.

Secondary Outcome Measures

- o General Medical/Psychiatric Health (*Time Frame: Baseline to 12 Weeks*) The Short Form-12 Health Survey (SF-12) will be used to assess self-report of emotional and physical functioning.
- Cognitive Testing (*Time Frame: Baseline to 12 Weeks*)
 - o Verbal learning/memory, attention, working memory, and complex decision-making will be assessed.

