- Brain-based Measures (*Time Frame: Baseline to 1 Year*)

- Changes in resting state functional connectivity and task-associated activation in brain regions involved in reward, inhibitory control, and working memory will be assessed.

The IRB protocol includes exploratory outcomes that were not presented in this manuscript, but will be included in future publications.

Statistical Analysis: The IRB protocol did not include the final statistical plan. When we brought [name], an experienced clinical trial statistician, on this project in Year 2 of the study, well before any analysis had been conducted, he suggested that instead of a random slopes analysis that assumes the effect of the drug will be to gradually increase the effect or outcome, ie a time x treatment interaction, he suggested we should assume a constant treatment effect over the follow up period, 2 weeks, 1 month, 3 months. [name] also advised us not to adjust for covariates as we originally proposed to do, but to only adjust for baseline symptoms, since randomization should have accounted for differences and we had no strong prior information about what covariates would have an important effect on CUD in people seeking cannabis for medical complaints. [name], without access to the data, made these recommendations to Drs [name] and [name] after which [name], who had access to the data, implemented the analyses.

Propensity score analysis for missing data: We could not ensure that participants in the MMC condition obtained an MMJ card, and we could not give participants a MMJ card because of state and hospitals regulations, a stated limitation of the study. Thus, we conducted a post hoc sensitivity analysis to verify the positive findings of the primary analysis in the final stages of the analysis when we realized that there was a problem with differential drop-out between the randomization and the baseline visit in the MMC and WLC groups.

Sample size calculation:

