When participants in the active study group receive their medical marijuana card, they will be scheduled for a baseline assessment in which they will undergo cognitive testing, interviews, questionnaires, and possibly an MRI scan (see Measures below). In contrast, participants in the waitlist control group will be scheduled for the baseline visit approximately 3-4 weeks following the screening visit. All participants will then be scheduled for repeat assessments at approximately 2 weeks, 1 month, 3 months, 6 months and 1 year after the baseline visit. All participants will receive monthly check in phone calls from a research coordinator at approximately 2, 4, 5, 7-11 months past baseline in order to update study staff on medication changes, recent substance use, and overall physical and mental health. Participants will also be asked to complete a 2-year follow-up phone call, which is identical to previous check in calls, with the addition of the CGI and CUD checklist. If participants are in the active study group, we will ask that they not use MM on the day of testing (though they can use it after testing on that day). These visits will take approximately 3 hours to complete.

In consultation with their prescribing physician, participants in the waitlist control group will be asked to wait to start using MM until they have completed Visit 5 (Three Months). During those 3 months, they will be assessed at the same time points as those in the active MM group (see study schema). After the 3-month waitlist period, the waitlist control group will have the option to start using MM. If this group fails to adhere to the waitlist control, they will be kept in the study and will be asked to complete the same assessment schedule as those initially assigned to the active study group. All participants will be assessed after 1 year.

Measure	Instrument	Visit 1	Visit 2	Visit 3	Visit 4	Visit 5	Visit 6	Visit 7
		Screen	Baseline	Two Weeks	One Month	Three Months	Six Months	One Year
General Medical/Psychiatric Health								
Medical History/ CON MEDS		x	x	x	x	x	x	x
Quantitative cannabinoids			x	x	x	x	x	x
Drug Screen/pregnancy		x	x	x	x	x	x	x
Psychiatric Interview	MINI 7 + Past SUD and AUD	x						x
Suicidality and Health Risk Taking	CHRT	x	x	x	x	x	x	x
Emotional and physical Functioning	SF-12		x	x	x	x	x	x
ADHD symptoms	ASRS		x					x
Impulsivity	BIS-11		x			x	x	x
Executive function	BRIEF		x			x	x	x
Risk perceptions and behavior	DOSPERT		x			x		

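### The post hoc drop-out check is documented as confirming positive results, although the loss before baseline can bias any of the four primary outcomes in either direction

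*Combined protocol and SAP*

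**What the plan says.** The relevant text is in the combined protocol and SAP, in the Summary of Changes Made and Rationale.

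- **Trigger.** Under the propensity-score item, the investigators report that "there was a problem with differential drop-out between the randomization and the baseline visit in the MMC and WLC groups".
- **Response and purpose.** In the same sentence: "we conducted a post hoc sensitivity analysis to verify the positive findings of the primary analysis". No other purpose is given, and no outcome is named.
- **Timing.** The opening paragraph says "No changes were made after looking at the data, except for the propensity score analysis". The analysis is openly labelled post hoc.
- **Primary outcomes.** Four are listed: the number of CUD symptoms, and three that apply to participants with the relevant complaint ("For those with depression and anxiety symptoms, the Hospital Anxiety and Depression Scale will be used to assess symptoms"; "For those with pain, the Brief Pain Inventory Severity Scale (BPI-S) will be used to assess levels of pain"; "For those with insomnia, the Athens Insomnia Scale will be used to assess symptoms"). All run from baseline to 12 weeks.
- **Primary model.** The Statistical Analysis item describes a constant treatment effect over follow-up, adjusted for baseline symptoms only.
- **Where the loss arises.** Section V, Study Design (Medical Marijuana Participants): "When participants in the active study group receive their medical marijuana card, they will be scheduled for a baseline assessment". The waitlist baseline visit is instead set at about 3 to 4 weeks after screening. Active-arm participants with no card progress at six weeks are discontinued, but a three-month visit is still scheduled.

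The only other mention of missing data is in the Analytic Plan, item (c), and concerns imaging.

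**The concern.** Loss before the baseline visit happens to a participant, not to an outcome. If the active-arm participants who obtained a card differ from those who did not, the retained arms are no longer the randomised arms for any of the four primary outcomes. Adjusting for baseline symptoms was justified by relying on randomisation to balance the rest, and that justification weakens equally for all four.

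Selection of this kind has no fixed direction. It can create an apparent effect or mask a real one. A check aimed at positive results guards against the first error and leaves the second open. Because the check was added after the data had been seen, tying its scope to positive findings makes the degree of scrutiny depend on the result.

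The trial sets a possible harm (CUD symptoms) against possible benefits (pain, sleep, mood), and the sample-size text says it was sized for both. A risk-benefit reading needs the same standard of evidence on each side.

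**Working it through.** **Step 1. Scope of the problem against scope of the check.** The problem affects everyone randomised who might not reach baseline, and hence all four primary outcomes. The documented check covers findings that were positive. No text bridges the two. This comparison carries the point and needs no arithmetic.

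**Step 2. Could the check cover all four?** The visit schedule in Section V collects the CUD checklist, BPI, AIS and HADS at Visit 1 (screening), before the loss. A model for reaching baseline could therefore use all four measures.

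**Step 3. Illustrative size.** The documents give no drop-out rate for either arm and no SD, so the rates and differences below are assumptions.

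Inputs from the Sample size calculation item: two-sided 0.05; power 84% (pain), 84% (depression and anxiety), 90% (insomnia); 33 per group. The stated powers cannot be reproduced without an SD, so the standardised effect is solved back from them:

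- SE = sqrt(2/33) = 0.246 SD
- 84% power: d = (1.960 + 0.994) × 0.246 = 0.73
- 90% power: d = (1.960 + 1.282) × 0.246 = 0.80

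If those lost differ from those retained by δ, the same in both arms, the contrast shifts by

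bias = (p_MMC − p_WLC) × δ

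- 25% against 5% lost, δ = 0.5 SD: 0.20 × 0.5 = 0.10 SD
- 40% against 5% lost, δ = 0.8 SD: 0.35 × 0.8 = 0.28 SD
- Difference wholly removed by baseline-symptom adjustment: 0 SD

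Here δ means what remains after that adjustment. With bias toward the null, power = Φ(d/SE − 1.960 − bias/SE). For the 84% outcomes this is Φ(0.994 − bias/0.246); for insomnia it is Φ(1.282 − bias/0.246). With no true effect, the two-sided error rate is Φ(bias/SE − 1.960) + Φ(−bias/SE − 1.960).

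| Bias (SD) | Power, pain or depression/anxiety | Power, insomnia | Error rate if no true effect |
|---|---|---|---|
| 0 | 84% | 90% | 5% |
| 0.10 | 72% | 81% | 6.9% |
| 0.20 | 57% | 68% | 12.8% |
| 0.28 | 44% | 56% | 20.6% |

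The middle columns show a true effect being hidden and the last shows a false one being created. The same bias does both, which is why checking one class of result is not enough.

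**Step 4. Limits of the illustration.** The SE is for equal groups, a single measurement and no adjustment. Allocation moved to 2:1 early in the trial. For the same 66 participants split 44:22, SE = sqrt(1/44 + 1/22) = 0.261 SD, and d = 0.73 starts at about 80% power before any bias. Baseline adjustment and repeated visits would act the other way.

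**The case against.** The strongest reply is that the text states a purpose and does not list the outcomes analysed. A reader might infer that null outcomes were left out, or that a null result on pain or mood went unchecked. The documents support neither. They contain no results, do not say which primary outcomes were positive, and never say that any was excluded. If all four were positive, the stated purpose already covers them all. This stands, and it limits the point to documented scope.

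The size can also be challenged. Only a difference that survives baseline-symptom adjustment causes bias, so the range must start at zero. The equal δ in both arms and the adverse direction are assumptions. It is tempting to say that a null symptom result could come from drop-out alone, but that goes too far: at 0.10 SD detection is still likely (72%), and a 16% chance of a miss exists with no bias at all. These objections stand too.

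It is also fair to say that the documents specify neither the form of the propensity-score analysis nor its covariates. Reusable participant weights cannot be assumed to exist.

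Finally, stress-testing claimed effects is a common use of a post hoc analysis, and this one is candidly labelled. That answers a charge of concealment, which is not made here. It does not explain why a bias that acts on every outcome should be examined according to how the outcome turned out.

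**Conclusion.** The point holds as one about documented scope. The only description of the drop-out check ties it to positive findings and was written after the data were seen, while the bias it addresses can reach all four primary outcomes in either direction. Following the stated scope would leave any non-positive primary outcome unexamined. Whether that happened, and to which outcomes, cannot be known from the documents.

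The size is illustrative: from no effect to a fall in power from 84% to 44%, with 72% in the middle case. It rests on assumed drop-out rates, an assumed residual difference common to both arms, bias toward the null, and 33 per group without adjustment. The recommendation does not depend on where in that range the truth lies. If all four outcomes were in fact checked, the text misdescribes the analysis and needs correcting; if not, the analysis needs completing.

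**What to change.** 1. Apply one propensity-score specification to all four primary outcomes, whatever their result, using the screening values of the CUD checklist, BPI, AIS and HADS. State the form of the analysis and its covariates.
2. Report the result beside each primary estimate, with the numbers randomised and the numbers lost before baseline in each arm.
3. Where three-month data exist for discontinued active-arm participants, use them to examine how those lost compare with those retained.
4. Keep the post hoc label, and reword the purpose as assessing the effect of differential drop-out on all primary outcomes.

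The cost is a few extra model runs, a short table and one reworded sentence, with no new data collection. If the existing analysis did not produce reusable weights or scores, the model for reaching baseline has to be fitted again. The downside is that some primary results may look less robust.

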This was not included in the trial protocol but calculated for the R01 grant submission in 2016. We aimed to recruit 200 participants in order to have sufficient power to detect benefits and risks of MMCs. To identify a difference in development of CUD symptoms in the MMC vs WLC groups, assuming that the mean number of symptoms for MMC would be .4 (corresponding to 20% of subjects developing CUD) versus .1 in WLC (corresponding to 5% of subjects developing CUD), at a two-sided 0.05 significance level, power was 85%. To identify a difference in symptoms of pain, insomnia, depression, and anxiety, assuming a clinically significant effect would be a 30% reduction in presenting medical symptom with MMC while WLC subjects were expected to have a minimal change, assumed to be a 5% reduction, at a two-sided 0.05 significance level, based on effect sizes in the literature, power was 84% (pain), 90% (insomnia), and 84% (depression and anxiety), with sample sizes of approximately 1/3 (33 in each group) in the pain, insomnia, and anxiety/depression subgroups.

PARTNERS HUMAN RESEARCH COMMITTEE

DETAILED PROTOCOL: Effect of Medical Marijuana on Neurocognition and Escalation of Use

Protocol #: 2015P001600

Principal Investigator: [name].

Co-Investigator: A. [name]

Version Date: 04/15/2020

I. BACKGROUND AND SIGNIFICANCE

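### The stated powers for the three symptom outcomes belong to a 33 vs 33 design that the trial replaced with 2:1 allocation, and the target sample size is given as both 200 and 400 in total

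*Combined protocol and SAP*

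**What the plan says.** All references are to the combined protocol and SAP.

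- **Summary of Changes, Sample size calculation.** The target is stated as "We aimed to recruit 200 participants in order to have sufficient power to detect benefits and risks of MMCs". For the symptom outcomes the power statement reads "power was 84% (pain), 90% (insomnia), and 84% (depression and anxiety"), and the arm sizes behind it are given as follows: "with sample sizes of approximately 1/3 (33 in each group) in the pain, insomnia, and anxiety/depression subgroups". The planned contrast is a 30% reduction with MMC against 5% with WLC, at two-sided 0.05. The standardised effect is attributed to the literature and no SD is given. On its origin: "This was not included in the trial protocol but calculated for the R01 grant submission in 2016".
- **Summary of Changes, Method of randomization.** "We therefore changed our randomization from 1:1 to 2:1 MMC:WLC early in the trial".
- **Summary of Changes, Statistical Analysis.** The final analysis is to "assume a constant treatment effect over the follow up period, 2 weeks, 1 month, 3 months" and "to only adjust for baseline symptoms".
- **Summary of Changes, Propensity score analysis for missing data.** There was "differential drop-out between the randomization and the baseline visit in the MMC and WLC groups". No rate is given.
- **Section V, Study Procedures, Medical Marijuana Participants (Screening).** The plan is 200 randomised to each of the two arms.
- **Section VI, Participant Enrollment.** The number to be enrolled is 400.
- **Analytic Plan, Power/Sample Size.** 80 per group are needed for the cannabis use disorder (CUD) outcome.

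**The concern.** Pain, insomnia, and depression and anxiety make up three of the four primary outcomes, and these are the only powers the documents give for them. They are tied to equal arms, yet the same summary says that equal allocation was abandoned early. For a fixed total, unequal arms give a less precise comparison. A reader who takes 84%/90%/84% as describing the 2:1 trial is therefore reading figures for a different allocation.

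The target size adds to the difficulty. The powers rest on 200 in total, but the attached protocol, version dated 04/15/2020, plans for twice that number in two equal arms. The documents do not settle which total and which allocation the power statement should be read against.

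**Working it through.** **Inputs.** Two-sided alpha 0.05; 33 vs 33; stated powers 84%, 90% and 84%; total 200; allocation 2:1. All are from the Summary of Changes. No SD is given.

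**1. What 33 per arm implies.** 3 subgroups × 2 arms × 33 = 198 of 200. Almost every recruit is counted as analysed. That there is no loss allowance is an inference from this arithmetic; the text does not say so.

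**2. The plan's own figures.** Without an SD they cannot be reproduced independently, so the standardised effect d was solved from them. For a two-sample t test the noncentrality is d / √(1/n₁ + 1/n₂).

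- At 33 vs 33, 1/33 + 1/33 = 0.0606.
- 84% power requires d = 0.738; 90% requires d = 0.810.
- For a 25-point difference in percentage reduction these correspond to SDs of 25/0.738 ≈ 34 and 25/0.810 ≈ 31 points.

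**3. Same effects and same 66 per subgroup at 2:1.** 66 splits into 44 vs 22, and 1/44 + 1/22 = 0.0682. The variance ratio to 33 vs 33 is 0.0682/0.0606 = 1.125.

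| Arms (MMC vs WLC) | Pain | Insomnia | Depression and anxiety |
|---|---|---|---|
| 33 vs 33 (stated) | 84% | 90% | 84% |
| 44 vs 22, no loss | 79.5% | 86.4% | 79.5% |
| 40 vs 26, no loss | 82.3% | 88.6% | 82.3% |

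The second row is 4.5, 3.6 and 4.5 points below the first. The third row illustrates a share of participants randomised 1:1 before the change; the documents do not give that share.

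**4. Why this is not the power of the trial as run.** Each item below adds an assumption that the documents do not supply.

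- *Final model.* Suppose d refers to one unadjusted follow-up score, all three follow-up visits are complete, and every pair of visits has correlation r. Adjusting the mean of the three visits for baseline multiplies the variance by (1 − r)(1 + 3r)/3, which is 0.443, 0.417 and 0.310 at r = 0.3, 0.5 and 0.7. Power at 44 vs 22 is then 98.7% to 99.9% (pain, depression and anxiety) and above 99.5% (insomnia). If d refers to a change score, the factor is (1 + 3r)/6; at r = 0.7 it is 0.517 and power is 97%/99%. If the planning figures already reflected the final model, there is no such gain.
- *Larger total.* One third of 400 is about 133, or 89 vs 44 at 2:1. Unadjusted power is about 98% (pain, depression and anxiety) and 99% (insomnia).
- *Loss.* With an assumed 30% loss in MMC only, 44 becomes 31. Unadjusted power at 31 vs 22 is 74%/81%/74%.

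**5. Target size.**

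| Place | Number | Total |
|---|---|---|
| Summary of Changes, Sample size calculation | 200 overall | 200 |
| Section V, Screening | 200 per arm | 400 |
| Section VI | 400 enrolled | 400 |

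Sections V and VI agree with each other (2 × 200 = 400) and conflict with the summary. Equal arms of 200 are also a 1:1 split, which does not fit 2:1.

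**The case against.** The strongest reply is that nothing is hidden. The power sentence itself gives the arm size, the paragraph dates the calculation to 2016, and the change of allocation, the drop-out and the new model are all disclosed nearby. Reporting an original planning calculation unaltered is defensible. By the cover date of January 2022 a primary analysis existed, so restated power could change no design decision. This stands in part: it limits the point to labelling and consistency. It does not remove it, because no sentence says that the powers no longer match the allocation.

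On the target size, the summary says that the protocol was written for a pilot phase and that sample size calculations were up to date in the registry. This is a partial link only. The summary also says that the protocol was updated when the R01 was received, and the version dated 2020 still carries 200 per arm and 400. The registry record was not available for this review.

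Four stronger readings are tempting, and the documents do not support them:

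- *The trial was underpowered.* The final model or a total of 400 could put power well above the stated values. The loss rate is unknown, and leaving before baseline is not automatically lost outcome data: Section V schedules a three-month visit for participants discontinued for lack of progress towards a card, and the symptom scales are also collected at screening.
- *The powers were miscalculated.* With no SD stated, they cannot be shown to be wrong.
- *The move to 2:1 was a mistake.* With MMC retention s and complete WLC retention, the two allocations have equal variance when 1/(44s) + 1/22 = 1/(33s) + 1/33, that is s = 0.5. If about half or more of the MMC arm was lost, 2:1 would be no worse than 1:1.
- *80 per group is a third competing target.* It is a minimum for CUD only.

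**Conclusion.** The point holds as an inconsistency between the stated power, the stated sample size and the design described in the same documents. The 84%/90%/84% belong to 33 vs 33. At 44 vs 22 the like-for-like figures are about 79.5%/86.4%/79.5%, with a smaller drop if some participants were randomised before the change.

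Those figures rest on effects back-solved from the stated powers, an unadjusted two-sample comparison, 66 per subgroup, 2:1 holding within each subgroup, and no loss. They do not establish a net loss of power: the direction for the trial as run cannot be settled from the documents. The conflict between 200 and 400 in total needs no assumption. The point is minor to moderate; it should be corrected, but it does not by itself call the trial's results into question.

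**What to change.** 1. In the Summary of Changes, Sample size calculation, label 84%/90%/84% as the 2016 planning figures for 1:1 allocation with no allowance for loss.
2. Beside them, give the corresponding figures at 2:1. Either use about 80%/86%/80%, marked as same-assumption, unadjusted and without loss, or give the sponsor's own recalculation under the final model with its inputs stated. Use the planning effects, not the observed ones.
3. Reconcile the Sample size calculation paragraph, Section V (Screening) and Section VI to one target number and one allocation, and say in one sentence how the pilot-phase and R01 numbers relate.

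The cost is a few sentences and a short calculation. The figure shown may be 3.6 to 4.5 points less favourable on the like-for-like basis, or more favourable under the final model. No extra enrolment or data collection is needed.
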